6.2.1 Screening and baseline periods

Visit 1/Day -1 – Screening/baseline visit

Informed consent and authorization to release protected health information must be obtained prior to any trial related procedures taking place.

Tests for which results are not already available as part of the patient’s standard of care, may be ordered after the patient signs informed consent.

Prior to starting study medication the investigator should: 1) review all information obtained at this visit, 2) review the inclusion/exclusion criteria and 3) confirm that the patient has discontinued all prohibited therapy or medications (see [Sections 4.2.2](#) and [4.2.2.1](#)) and an adequate washout period has passed.

Table 6.2.1: 1 Visit 1 / – Screening visit and baseline visit

	The following must be performed and information recorded in the patient’s chart	What to include in eCRF
Informed Consent	Written informed consent and authorization to release protected health information must be obtained prior to any trial related procedures taking place.	Date of informed consent
Demographics	Obtain the following demographic data: sex, birth date, race, smoking and alcohol history	Sex, birth date, race, ethnicity, and smoking history
Medical history	Oncological and relevant non-oncological history including details of previous treatment for NSCLC (including pathology)	
 • History of NSCLC: • Oncological and relevant non-oncological history including details of any previous treatment for NSCLC • The date of first histological diagnosis, the primary tumour site, the number and location of metastatic sites (bone, brain, liver, pleural effusion, other) • Tumour assessment/stage at the time of diagnosis according to the TNM-classification • Previous surgeries for NSCLC • Previously administered chemo-, immuno-, hormone therapy will be reported including start and end dates, the treatment regimen with the number of courses (chemo-, immunotherapy), the best response obtained (complete response, partial response, stable disease, progressive disease, unknown), and progression date. • Previous radiotherapy - the total radiation dose and radiation field will be recorded

Proprietary confidential information.

© 2019 Boehringer Ingelheim International GmbH or one or more of its affiliated companies. All rights reserved.

This document may not - in full or in part - be passed on, reproduced, published or otherwise used without prior written permission.

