## **7.7 EXTENT OF EXPOSURE**

Total treatment time (days) will be calculated for each patient; total treatment time will include any dose interruptions or off-drug periods.

The definition of exposure is:

Treatment stop date – treatment start date + 1

In case of death due to any cause, the treatment stop date will be imputed as the earlier of (date of last administration of afatinib treatment, date of death) + 1 day

Standard descriptive summaries of these data will be provided for the treated set of patients.

Total treatment time (days) will be summarized by afatinib dose level (40 mg, 30 mg, 20 mg and total), and by number of therapy lines. The number of therapy lines for afatinib will be

derived as: the number of all previous therapy lines + 1. The number of all previous therapy lines that the patient received prior to the start of the treatment includes number of lines of all of the following:

- Systemic chemotherapies: count the number of previous chemotherapies obtained from the field “Line of therapy” on the previous chemotherapies eCRF page .
- Other anti-cancer therapies: count the number of anti-cancer therapies obtained from the field “Line of therapy” on the other anti-cancer therapies eCRF page. If there is a therapy with the same name and same start and end dates as a therapy present in Systemic chemotherapies eCRF page, then ignore this as it has already been counted earlier.

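### SAP 7.7 adds therapy lines over two eCRF pages, so one prior regimen entered on both pages can count as two lines and move a second-line patient to a later-line row

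*SAP*

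**What the plan says.** SAP 7.7 plans this summary: "Total treatment time (days) will be summarized by afatinib dose level (40 mg, 30 mg, 20 mg and total), and by number of therapy lines". For that table, the afatinib line is "derived as: the number of all previous therapy lines + 1". The number of previous lines "includes number of lines of all of the following", and two sources are named:

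- The first source is the chemotherapy page, with the instruction "count the number of previous chemotherapies obtained from the field “Line of therapy” on the previous chemotherapies eCRF page".
- The second source is the page for other agents, with the parallel instruction "count the number of anti-cancer therapies obtained from the field “Line of therapy” on the other anti-cancer therapies eCRF page".

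One exception is attached to the second source. It begins "If there is a therapy with the same name and same start and end dates as a therapy present in Systemic chemotherapies eCRF page", and such an entry is then ignored because it was counted under the first source.

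Protocol Table 6.2.1: 1 describes what is collected at screening: "Previously administered chemo-, immuno-, hormone therapy will be reported including start and end dates, the treatment regimen with the number of courses". Protocol 3.3.3 excludes any prior EGFR-TKI, but bars other anti-cancer treatment only in the 2 weeks before the start of trial treatment. Patients with earlier systemic therapy can therefore enter. SAP 7.1 lists systemic chemotherapies and other anti-cancer therapies as separate baseline items, which fits two separate pages.

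**The concern.** A line of therapy is a treatment episode, and one episode may contain several agents. The SAP forms a count on each page and adds the two. Its exception shows that overlap between the pages was foreseen, but it covers only the exact repeat of one entry. Two agents of one regimen have different names, so the exception cannot apply to them even when their dates are identical. A true repeat entry also escapes if a start or end date differs by one day.

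In both cases a single earlier line is counted twice, and the patient appears one row later in the table of treatment time. The second-line row loses patients, and later rows gain patients who are earlier in their treatment course than the label says. If the later-line rows are small, a few misplaced patients could change their summary statistics noticeably.

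**Working it through.** The plan gives no figure to reproduce. The check applies the stated rule to simple treatment histories.

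**Inputs.** The two page counts, the exception and the added 1 all come from SAP 7.7. The planned size of about 500 comes from Protocol 3.3 and serves only for scale.

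**Formulas.** Let C be the set of distinct Line of therapy values on the chemotherapy page. Let O be the set on the other page after removing entries with identical name, start date and end date.

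- SAP rule, read literally: line = (number in C) + (number in O) + 1.
- Comparison: line = (number of distinct values over both pages combined) + 1.

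Where exact repeats carry the same line value on both pages, the SAP result exceeds the comparison by the number of line values found in both C and O. That number cannot be negative, so the error cannot move a patient to an earlier line.

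**Results, with lines numbered on one scale across both pages.**

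| Prior therapy as entered | SAP rule | Distinct lines + 1 |
|---|---|---|
| None | 0 + 0 + 1 = 1 | 0 + 1 = 1 |
| Chemotherapy only, line 1 | 1 + 0 + 1 = 2 | 1 + 1 = 2 |
| Chemotherapy and another agent, both line 1, same dates | 1 + 1 + 1 = 3 | 1 + 1 = 2 |
| The same, with the other agent continued longer | 1 + 1 + 1 = 3 | 1 + 1 = 2 |
| Identical entry on both pages | 1 + 0 + 1 = 2 | 1 + 1 = 2 |
| Same therapy on both pages, end dates one day apart | 1 + 1 + 1 = 3 | 1 + 1 = 2 |
| Chemotherapy line 1, then another agent line 2 | 1 + 1 + 1 = 3 | 2 + 1 = 3 |
| Combined line 1, then chemotherapy line 2 | 2 + 1 + 1 = 4 | 2 + 1 = 3 |

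The rules agree for untreated patients, for therapy on one page only, for exact repeats and for truly sequential therapy. They differ by one line for each regimen split over the pages and for each near-duplicate.

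**Scale.** The documents give neither the share of pretreated patients nor the share with a split regimen. As a pure assumption, if 0%, 1%, 5%, 10% or 20% of 500 patients were affected, 500 × share gives 0, 5, 25, 50 or 100 patients.

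**The case against.** The strongest objection is that the error depends on an eCRF that is not shown. Protocol Table 6.2.1: 1 asks for the treatment regimen and number of courses. If a combination is entered once, as a regimen on the chemotherapy page, no splitting occurs. This stands as a limit on frequency: the number affected may be zero. It does not mend the rule, which has no provision for a regimen that is entered on both pages.

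Second, the wording is loose. It speaks of lines and takes them from the Line of therapy field, so a programmer might count distinct values over both pages. The text does not say this. It defines a separate count for each page, and an exception based on names and dates would be largely redundant under that reading. SAP 7.8.1 mentions a technical TSAP for adverse-event groupings. Whether it also treats therapy lines cannot be seen.

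Third, a distinct-value count is right only if both pages share one numbering. If each page starts again at 1, chemotherapy followed by another agent would give 1 + 1 = 2 under that count, while the SAP sum gives the correct 1 + 1 + 1 = 3. This stands, and the fix has to allow for it.

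Finally, a reader might infer that the whole exposure-by-line analysis is wrong, or that the comparison of first-line with pretreated patients is distorted. The documents do not support that. An untreated patient is line 1 under either rule, and a patient with a split regimen is pretreated under either rule.

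**Conclusion.** The point holds within narrow limits. As written, SAP 7.7 counts one prior regimen as two lines when its components are entered on both pages under different names, or when a repeated entry has slightly different dates. Each such case moves the patient one line later.

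Only the second-line and later rows of the descriptive treatment-time table can shift. The first-line row, the first-line versus pretreated contrast, the overall exposure summary, the primary endpoint (patients with SAEs) and overall TTSP do not depend on the rule. SAP 6.4, to which SAP 7.1 refers for subgroup variables, is not in the text available, so any wider use of therapy line can be neither confirmed nor excluded.

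The conclusion rests on a literal reading of SAP 7.7 and on some regimens being recorded on both pages with a common line number. A percentage for the misplaced share of the second-line row would only restate an assumed rate of split regimens. Priority is low to moderate: the rule is demonstrably incomplete, its reach is small, and it is cheap to correct.

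**What to change.** First confirm from the eCRF and its completion instructions that Line of therapy is numbered on one scale across the two pages. Then amend SAP 7.7 along these lines:

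- Previous lines = number of distinct Line of therapy values over the systemic chemotherapy and other anti-cancer therapies pages combined. Afatinib line = that number + 1.
- Where line values are missing, discordant or numbered separately by page, entries with overlapping dates count as one line. Entries that do not overlap count as separate lines.

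The same-name, same-dates exception may stay. It is redundant when the line values agree, and it still catches an exact repeat that carries two different line numbers. The same derivation should be used wherever therapy line is summarised.

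The cost is a few sentences in the SAP and a short programming change. The Line of therapy field is already on both pages and the Protocol already asks for therapy dates, so no new data are needed. A listing of patients for whom the two derivations differ would show at once whether the issue matters in this trial.

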## **7.8 SAFETY ANALYSIS**

All safety analyses will be performed on the treated set.

### **7.8.1 Adverse events**

The intensity of adverse events were classified and recorded according to the Common Terminology Criteria for Adverse Events (CTCAE) version 3.0 in the eCRF.

Unless otherwise specified, the analyses of adverse events will be descriptive in nature. All analyses of AEs will be based on the number of patients with AEs and NOT on the number of AEs.

Furthermore, for analysis of AE attributes such as duration, severity, etc. multiple AE occurrence data on the CRF, will be collapsed into AE episodes provided that all of the following apply:

- The same MedDRA lowest level term was reported for the occurrences
- The occurrences were time-overlapping or time-adjacent (time-adjacency of 2 occurrences is given if the second occurrence started on the same day or on the day after the end of the first occurrence)
- Treatment did not change between the onset of the occurrences OR treatment changed between the onset of the occurrences, but no deterioration was observed for the later occurrence

For further details on summarization of AE data, please refer to the guideline 'Handling and summarization of adverse event data for clinical trial reports and integrated summaries' ([2](#)) [001-MCG-156]

The analysis of adverse events will be based on the concept of treatment emergent adverse events. That means that all adverse events occurring between first study drug intake until 28 days after last study drug intake will be assigned to be treatment-emergent. All AEs occurring outside of this period will be handled according to the treatment definition period definitions detailed in [Section 6.1](#) and will only be listed unless stated otherwise.

An overall summary of adverse events will be presented. This summary will exclude the rows ‘Severe AEs’, ‘Significant AEs’ and ‘Other significant AEs’ but will include additional

rows for 'AEs leading to dose reduction' and 'AEs by highest Common Terminology Criteria (CTC)' grade.

The frequency of patients with adverse events will be summarised by highest CTC grade (grades 3, 4, 5 and all grades including also grade 1 and 2), treatment, primary system organ class (SOC) and preferred term (PT) for each of the following AE tables:

- All AEs collected
- Drug related AEs.
- AEs leading to dose reduction.
- AEs leading to treatment discontinuation.
- Drug related AEs leading to treatment discontinuation
- Serious AEs.
- Drug related serious AEs.
- AEs leading to death.

All tables will be sorted by SOC according to the standard sort order specified by the European Medicines Agency (EMA); PTs will be sorted by frequency (within SOC).

The above tables except for AEs leading to death will be repeated with the project defined grouping of AE terms (rash, stomatitis, ocular effects, lip effects, nail effects and fatigue). Details of the project defined groupings are defined in the technical TSAP. In these tables the grouped AEs will replace the original PTs for all AEs that are included within the grouped term. The grouped AE categories will then be tabulated along with all remaining MedDRA PTs, sorted by descending frequency. A reference table presenting all of the project defined groupings and MedDRA PTs within each grouping will also be produced.

Additional AE tables will be produced for AEs of special interest (diarrhoea, and the project defined groupings of rash and renal insufficiency), providing further details on highest CTC grade, action taken with study drug and time to first onset of AE.

Number of patients with adverse events with incidence greater than 5% will be summarised by treatment, primary system organ class (SOC) and preferred term (PT).

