Worsening of the underlying disease or of other pre-existing conditions will be recorded as an (S)AE in the eCRF.

If progressive disease occurs and is associated with symptoms, the term “Progressive Disease” should not be reported as AE, however, signs and symptoms of progressive disease will be reported as an (S)AE (if applicable). Exception to this: Death due to progressive disease and where no signs or symptoms are available should be reported as “malignant neoplasm progression (grade 5, outcome fatal).”

Changes in vital signs, physical examination, and laboratory test results

Changes in vital signs, physical examination and laboratory test results will be recorded as an (S)AE in the (e)CRF, if they are judged clinically relevant by the investigator.

If the investigator determines any protocol-specific significant event is related to trial drug, the administration of the trial drug must be managed according to [Section 4.1.4.1](#) of the protocol.

Expected Adverse Events

Proprietary confidential information.

© 2019 Boehringer Ingelheim International GmbH or one or more of its affiliated companies. All rights reserved.

This document may not - in full or in part - be passed on, reproduced, published or otherwise used without prior written permission.

For expected (listed) AEs of afatinib, see the current version of the IB ([c01617169-04](#)).

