7.3.3 Safety analyses

All treated patients will be included in the safety analysis. In general, safety analyses will be descriptive in nature and will be based on BI standards. No hypothesis testing is planned.

Statistical analysis and reporting of adverse events will concentrate on treatment-emergent adverse events. To this end, all adverse events occurring between first drug intakes until 28 days (inclusive) after last treatment administration will be considered 'treatment-emergent'. Adverse events that start before first drug intake and deteriorate under treatment will also be considered as 'treatment-emergent'.

Frequency, severity, and causal relationship of adverse events will be tabulated by system organ class and preferred term after coding according to the current version of the Medical Dictionary for Drug Regulatory Activities (MedDRA).

Adverse events will be graded according to CTCAE, Version 3.0 ([R04-0474](#)).

CTC grades will be applied to laboratory parameters using the current BI oncology standard as detailed in the document 'Conversion of laboratory parameters to CTCAE grades within BI.'

Vital signs, physical examinations, or other safety-relevant data observed at screening, baseline, during the course of the trial and at the end-of-trial evaluation will be assessed with regard to possible changes compared to findings before start of treatment.

Proprietary confidential information.

© 2019 Boehringer Ingelheim International GmbH or one or more of its affiliated companies. All rights reserved.

This document may not - in full or in part - be passed on, reproduced, published or otherwise used without prior written permission.

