### **3. INTRODUCTION**

As per ICH E9, the purpose of this document is to provide a more technical and detailed elaboration of the principal features of the analysis described in the protocol, and to include detailed procedures for executing the statistical analysis of the primary and secondary variables and other data.

This TSAP assumes familiarity with the Clinical Trial Protocol (CTP), including Protocol Amendments. In particular, the TSAP is based on the planned analysis specification as written in CTP Section 7 “Statistical Methods and Determination of Sample Size”. Therefore, TSAP readers may consult the CTP for more background information on the study, e.g., on study objectives, study design and population, treatments, definition of measurements and variables, planning of sample size, randomization.

SAS® Version 9.4 will be used for all analyses.

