#### **4. CHANGES IN THE PLANNED ANALYSIS OF THE STUDY**

The definition of time to symptomatic progression (TTSP) has been clarified in [Section 7.5.2](#).

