## **6. GENERAL ANALYSIS DEFINITIONS**

### **6.1 TREATMENT**

There is only one treatment in this study, which is afatinib. The starting dose for all patients is 40 mg with an option to reduce the dose to 30 mg or 20 mg based on individual tolerability. Unless otherwise stated, for all analyses, treated patients will be presented under the starting dose.

The following study periods based on key visit dates and actual start and stop dates of study treatment administration are defined:

- Screening: From day of informed consent to day prior to starting study treatment.

Special handling rule:

If informed consent date = date of first administration of active treatment in the trial, derive start of screening phase on the day of informed consent – 1 day.

- On-treatment: From day of first administration of study treatment to the day of last administration of study treatment.
- Residual effect period (REP): From day after last administration of study treatment to the 28th day after last administration of study treatment.
- Follow-up: After the residual effect period and up to the last per protocol contact.
- Post-study: After the last per protocol contact but entered in the database before database lock.

For safety summaries data recorded up to 28 days after last administration of study treatment will be considered as on-treatment (i.e. the actual on-treatment and REP periods defined above will be combined into one 'on-treatment' analysis period).

Safety data recorded after follow-up period will be listed as post-study events but not tabulated.

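### SAP 7.8.1 drops, without declaring it, the protocol rule that pre-dose adverse events worsening on treatment are treatment-emergent, so the primary SAE count can fall below the protocol's

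*SAP*

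**What the plan says.** Protocol 7.3.3 gives two routes to treatment-emergent status. The first is a window from first intake to 28 days (inclusive) after the last administration. The second adds: "Adverse events that start before first drug intake and deteriorate under treatment will also be considered as" treatment-emergent.

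SAP 7.8.1 gives the first route only: "all adverse events occurring between first study drug intake until 28 days after last study drug intake will be assigned to be treatment-emergent". Events outside that period are assigned to the study periods of SAP 6.1 "and will only be listed unless stated otherwise". SAP 6.1 defines the pre-dose period as "Screening: From day of informed consent to day prior to starting study treatment".

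SAP Section 3 says that "the TSAP is based on the planned analysis specification as written in CTP Section 7". SAP Section 4 declares one change: "The definition of time to symptomatic progression (TTSP) has been clarified in" Section 7.5.2. The SAP history table does not list 7.8.1 among the sections revised in March 2017.

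The primary endpoint is the number of patients with SAEs (Protocol 5.2.1, SAP 5.1), and SAP 7.4 refers its analysis to Section 7.8. AEs and SAEs are collected from informed consent (Protocol 5.2.2.2), so events that start before dosing are in the database.

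**The concern.** The two governing documents define differently which events enter the primary count, and nothing visible in the SAP acknowledges it. A programmer working from the protocol and one working from the SAP could report different numbers of patients with SAEs from the same data.

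The direction is fixed. The SAP's rule is the protocol's rule with one route removed, so where the counts differ the SAP's is lower. In a single-arm trial whose primary objective is safety, any discrepancy understates the main result.

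The secondary count of patients with drug-related AEs is unlikely to move. Protocol 2.3 reports that almost all afatinib patients had diarrhoea within two weeks, so nearly everyone would be counted for another event anyway.

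**Working it through.** The plan states no figure to reproduce: Protocol 7.6 gives no formal sample size calculation, and no hypothesis is tested. The check therefore applies both rules to test cases and then sizes the difference.

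**Step 1. Both rules applied to four cases, reading the SAP window by onset date.**

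| Case | Protocol 7.3.3 | SAP 7.8.1 |
|---|---|---|
| A. Onset Day -5, becomes serious Day 10, one record | counted | listed only |
| B. Same event on two records, the second starting Day 10 | counted | counted |
| C. Serious, onset Day 3 | counted | counted |
| D. Serious, onset Day -5, no worsening | not counted | not counted |

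The documents differ only in case A.

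**Step 2. Whether another provision covers case A.**

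- Protocol 5.2.2.1 says: "Worsening of the underlying disease or of other pre-existing conditions will be recorded as an (S)AE in the eCRF". This helps if the worsening is entered as its own record, which makes it case B. The sentence does not say that worsening of an AE already open on the eCRF needs a new record with a new onset date.
- The SAP's collapsing rule merges occurrences across a treatment change only when there was a change "but no deterioration was observed for the later occurrence". A worsened later occurrence therefore stays separate and is counted. The rule applies to multiple occurrences, so it does not reach a single record.

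**Step 3. Size.** Inputs:

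- N = 500 (Protocol synopsis).
- Illustrative SAE rate p = 0.288, the afatinib arm of trial 1200.32 (Protocol 2.3). Using it here is an assumption.
- k = number of patients with a case A event. The documents do not give it.

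One patient is 1/500 = 0.2 percentage points. A patient with another on-treatment SAE is counted regardless. If other SAEs are independent of the case A event (a second assumption), the expected loss is

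loss = k × 0.2 × (1 − 0.288) = k × 0.1424 points.

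| k (assumed) | Expected loss, points | Expected patients lost |
|---|---|---|
| 0 | 0 | 0 |
| 1 | 0.14 | 0.71 |
| 5 | 0.71 | 3.56 |
| 10 | 1.42 | 7.12 |

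The last row corresponds to 2% of 500 patients having such an event, all on single records. It is an upper illustration, not an estimate.

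**Step 4. Scale.** 0.288 × 500 = 144 patients. The exact (Clopper-Pearson) 95% interval for 144/500 is 24.9% to 33.0%, or about 4 points either side. Even the upper illustration is smaller than the sampling uncertainty.

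**The case against.** The strongest reply is that the SAP is incomplete rather than contradictory. Its sentence refers to events occurring in the window, not starting in it, and an event that turns serious on Day 10 could be said to occur then. The SAP is built on Protocol Section 7, so if no change was meant there was nothing to declare. This does not settle the matter. The protocol uses the same verb for its first route and still needed the second sentence, and the SAP sends everything else to listings.

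Three practical points do stand:

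- **eCRF layout.** Case A needs a single record with a pre-dose onset and some means of seeing that the worsening came after the first dose. If the record holds one grade with no dated change, the protocol rule cannot be programmed from it either. The eCRF is not in the documents.
- **A small pool.** Screening lasts at most 28 days and shares Visit 1 with baseline, and SAP 6.1 even has a rule for consent and first dose on the same day. In that interval an AE must start, later become serious on treatment, stay on one record and be the patient's only on-treatment SAE.
- **Unseen standards.** SAP 7.8.1 cites a sponsor guideline on summarising AEs (001-MCG-156), which may contain the missing rule. It is not available here, and the SAP's own explicit definition omits the rule.

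These points limit the likely effect. They do not put the second route back into the SAP.

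**Conclusion.** The concern holds. The SAP's definition is narrower than the protocol's, the difference is undeclared, and it reaches the primary endpoint. The disagreement is confined to events with onset between consent and first dose that worsen on treatment and are held as one record. The two counts agree if there are no such events or if every worsening is entered as a new record.

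The realistic effect is a fraction of a percentage point: at N = 500, 0.2 points for each affected patient with no other on-treatment SAE. The expected figure of 0.14 points per affected patient rests on the borrowed 28.8% rate and on independence. The number affected cannot be obtained from the documents.

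Because the analysis is descriptive and the events remain in listings, this is a fault of consistency and completeness in the primary figure. No test or decision rule is affected. It should be corrected, but it does not threaten the trial's conclusions.

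**What to change.** Restore the second route in SAP 7.8.1, with a matching note in SAP 6.1: an AE that starts before first intake and worsens between first intake and 28 days (inclusive) after last intake is treatment-emergent and enters the AE and SAE tables.

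State how worsening is identified from the eCRF, including for single-record events. One workable definition is an increase in CTCAE grade or a change to serious. This is a suggestion and is not in the protocol.

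If the sponsor intends the narrower rule, declare it in SAP Section 4 as a change from Protocol 7.3.3. If guideline 001-MCG-156 already contains the rule, say so explicitly in 7.8.1.

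The cost is a sentence or two of SAP text and a few lines of programming. No new data are needed if the eCRF dates changes in grade or seriousness. The reported SAE figure may become slightly less favourable.
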